### **Discontinuation criteria**

1. Participant's failure or decline to comply with the protocol requirements.
2. Deviation from the schedule of examinations and sampling for lab tests by  $\geq 1$  day.
3. The necessity to use medications not permitted in the study.
4. An adverse event requiring discontinuation of the study drug.
5. Patients who decide to withdraw early from the study due to lack of treatment efficacy or for any other reason.

6. Cases not stipulated in the protocol where the investigator decides that further participation may harm the patient.
7. Eligibility error.

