## Statistical Analyses

### *Samples*

Total set comprised all enrolled patients whose parents/adopters had signed the informed consent form for participation of a patient in the trial. This sample will consider all adverse events throughout the study, including those occurred prior to the study therapy. Any medically unfavourable events (conditions) recorded in patients from Total set after signing informed consent but before administration of the study product will be considered as concomitant conditions.

Sample of the patients receiving at least one dose of the study product will be used for the study drug safety assessment (Safety population), as any adverse events emerging after administration of the product will be recorded.

Full Analysis Set This sample will consist of all enrolled patients, except for those who met at least one of the following criteria:

- 1) failure to meet inclusion/non-inclusion criteria;
- 2) patient failing to take any dose of the study drug;
- 3) absence of any data on the patient after randomization.

This was the best set for the Intention-to-treat method, so it will be used in the Intention-to-treat efficacy analysis of the test therapy.

Unavailable/missing data (parameters/variants) will be completed by the Last Observation Carried Forward method (LOCF).

Per Protocol set. This sample includes all patients who completed the therapy as per the study protocol, without any missing visits or major protocol deviations. This set will be used in the Per Protocol efficacy analysis of the test therapy.

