1.8 where  $N_F$  – final sample size;  $N$  – result of calculation in cl. 1.6, i.e. scheduled number of patients completing the study per protocol;  $C_w$  – withdrawal coefficient.

2. Assumptions on expected clinical study effects:

2.1 The difference between proportions of the patients with recovery/improvement on days 2-7 (according to the patient’s diary) and on days 3 and 7 (according to objective medical examination) in Ergoferon group and Oseltamivir is expected to be  $\geq 0\%$ .

The minimum size of each group will be determined as follows:

Number of patients	Final analysis
Number of patients in both groups	158
including	
- number of patients in Ergoferon groups	79
- number of patients in Oseltamivir group	79

Taking into account that potential withdrawal of 20% patients during the screening and during the study, at least 198 patients (99 in Ergoferon and Oseltamivir group) should sign informed consent.

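### The Per Protocol set deletes patients who stop because treatment failed, so it can bias the non-inferiority comparison, in either direction

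*Combined protocol and SAP*

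**What the plan says.** Under Statistical Analyses, Samples, the Per Protocol set is defined by completion: "This sample includes all patients who completed the therapy as per the study protocol, without any missing visits or major protocol deviations". Its role is given as "This set will be used in the Per Protocol efficacy analysis of the test therapy".

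The Discontinuation criteria include three reasons tied to how the patient is doing:
- item 3: "The necessity to use medications not permitted in the study"
- item 4: "An adverse event requiring discontinuation of the study drug"
- item 5: "Patients who decide to withdraw early from the study due to lack of treatment efficacy or for any other reason"

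The Samples section also defines a Full Analysis Set of enrolled patients. It leaves out only those who failed the eligibility criteria, took no dose or have no data after randomisation. Of this set the plan says "so it will be used in the Intention-to-treat efficacy analysis of the test therapy", with gaps filled by last observation carried forward (LOCF).

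Evaluation of sample size frames the comparison as non-inferiority with a 20% margin. It gives 79 per arm and describes N as the "scheduled number of patients completing the study per protocol". The Study design section states that the trial is open-label. No section names the set that decides non-inferiority or says that the two analyses must agree.

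**The concern.** A patient who follows every instruction and then leaves because the drug is not working has not completed therapy, or has missed a later visit. Either way that patient is outside the Per Protocol set, and so are the days on which non-recovery was actually observed. Selection then rests on a post-randomisation event related to the endpoint, and the comparison is no longer between groups formed by randomisation.

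In a non-inferiority trial the two success rates must stay unbiased relative to each other, because a gap narrowed by selection can be read as evidence that the test product is close enough. Both patients and investigators know the treatment, so willingness to leave when doing poorly may differ between arms. The set also carries weight in the plan, because the sample size is counted on patients who complete per protocol.

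**Working it through.** **The plan's own figure.** The formula is N = [p_a(1−p_a) + p_b(1−p_b)] × (z_α+z_β)²/(θ−δ)². The plan gives δ = 20% (read as 20 percentage points), power 80%, and an expected difference of at least 0 (θ = 0 used). It gives no values for p_a and p_b. At two-sided 0.05 the multiplier is (1.960+0.842)²/0.20² ≈ 196.2. A common rate of 0.725 gives 2 × 0.725 × 0.275 × 196.2 ≈ 78.2, rounded up to 79. Common rates of about 0.721 to 0.726 give 79; a rate of 0.50 gives 99 and 0.80 gives 63. So 79 cannot be derived from stated inputs, although a rate near 72% is consistent with it. The inflation does reproduce: 79/(1−0.20) = 98.75, or 99 per arm, and 158/(1−0.20) = 197.5, or 198.

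**Effect of deleting failures.** Let p be the true success rate when every patient is counted, and w the fraction of failures who leave and drop out of the set. The expected Per Protocol rate is p/[p + (1−p)(1−w)]. For example, with p = 80% and w = 25% it is 0.80/(0.80 + 0.20 × 0.75) = 84.2%. With p = 60% and w = 25% it is 0.60/(0.60 + 0.40 × 0.75) = 66.7%. The gap falls from 20 to 17.5 points.

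**Direction.** For small equal w, each rate rises by about p(1−p)w. The gap therefore changes by w(p_c−p_t)(1−p_c−p_t), where c is oseltamivir and t is Ergoferon. With p_c above p_t, it shrinks if the two rates sum to more than 100% and widens if they sum to less.

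**Size.** The assumptions are a true gap of exactly 20 points, 99 treated per arm, only failures leaving, and non-inferiority declared when the upper Wald limit (z = 1.96) of control minus test is below 20 points. Each cell shows the expected Per Protocol gap and the simulated false non-inferiority rate (400,000 runs). With nobody removed the false rate is about 2.5%.

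| True rates, oseltamivir vs Ergoferon | 25%/25% of failures removed | 50%/50% | 25%/50% |
|---|---|---|---|
| 80% vs 60% | 17.5 points; 6% | 13.9; 19% | 9.2; 43% |
| 72% vs 52% | 18.3; 4% | 15.3; 11% | 9.0; 36% |
| 50% vs 30% | 20.8; 2% | 20.5; 2% | 11.0; 20% |

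At 40% vs 20%, equal removal widens the gap to 22.1 points (25%/25%) or 23.8 (50%/50%), with a false rate of about 1%.

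**Equal exits as a share of all patients.** Now let the same share d of each arm leave, all of them failures, so that the Per Protocol rate is p/(1−d). At 72% vs 52% with d = 20% in both arms the rates are 90.0% vs 65.0%. The gap is 25.0 points and the false rate 0.3% (normal approximation). This implies that 20/28 = 71% of oseltamivir failures leave but only 20/48 = 42% of Ergoferon failures. With 15% leaving oseltamivir and 25% leaving Ergoferon the gap is 15.4 points and the false rate 10.3%. With 25% and 15% it is 34.8 points and below 0.1%.

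**The case against.** A reader might infer that deleting failures always pulls the arms together and so favours non-inferiority, even when both arms lose failures at the same rate. The documents do not support that. They give no expected success rates and no exit rates by arm, and the working shows the gap widening at low success rates or when equal shares of all patients leave. The primary outcome is read on days 2-7, so the direction may differ between early and late days.

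A reader might also infer that the Per Protocol set is decisive because the trial is sized on it. Counting N on completers does not make that set primary, and no text says that it is.

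The strongest defence is the Full Analysis Set. It keeps eligible, dosed patients with any post-randomisation data, and LOCF carries someone who leaves unrecovered forward as unrecovered. That stands as real mitigation. It is incomplete, because LOCF can carry forward a favourable last value for a patient stopped by an adverse event, and because no rule lets this analysis overrule the Per Protocol result.

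The illustration is also generous to the concern. The 99 per arm are consents, and the 20% allowance covers screening losses as well. Some listed exits have no necessary link to efficacy, such as schedule deviation or eligibility error, and these are set to zero. The 43% figure at 80% vs 60% needs exits of 20% × 25% = 5% on oseltamivir against 40% × 50% = 20% on Ergoferon, a fourfold split that nothing in the documents predicts. At 50% vs 30%, removing half of the failures means exits of 25% and 35%, above the allowance.

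**Conclusion.** The concern holds as a conditional one. The exclusion rule depends on outcome, and that follows from the text without any numerical assumption. Its direction and size are not determined by the documents. On the assumed rates, equal removal of failures gives false non-inferiority between about 2% and 19% across the three rate pairs in the table; removal weighted towards Ergoferon gives about 20% to 43%. Removal weighted towards oseltamivir works against Ergoferon. These figures are illustrations of what the rule permits, not estimates for this trial.

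This should be fixed, but it does not by itself invalidate the plan, because a second efficacy analysis retains most of these patients. What keeps it important is that the plan leaves open which analysis supports the non-inferiority claim.

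**What to change.** Amend the Per Protocol definition in the Samples section:
- Eligible patients who followed the protocol until they left for lack of efficacy, an adverse event that stopped the drug, or need of a non-permitted medicine stay in the set. They count as not recovered/improved from that day.
- Exclusions are limited to deviations judged unrelated to outcome, such as eligibility error, wrong product, or non-adherence not prompted by response or an adverse event. They are fixed from the recorded reasons before database lock.
- Non-inferiority is claimed only if the Full Analysis Set and Per Protocol results agree.

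Discontinuation item 5 combines lack of efficacy with all other reasons for withdrawing, so the recorded reason must separate the two.

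The cost is wording; no visit, procedure or sample size changes. Per Protocol success rates will be slightly lower, and the set will lie closer to the Full Analysis Set and so offer less of a contrast with it.

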### *Evaluation of sample size*

The sample size was assessed in accordance with the following rules and assumptions:

1. Statistical assumptions:

- 1.1 Lack of clinically relevant superiority of reference product (oseltamivir) over test product (Ergoferon) is assumed, thus statistically meeting Non-Inferiority design:

$$\mathbf{H_0: Ef_{control} - Ef_{test} \geq \delta}$$

$$\mathbf{H_A: Ef_{control} - Ef_{test} < \delta,}$$

where  $\mathbf{Ef_{control}}$  – effect of reference product (oseltamivir),  $\mathbf{Ef_{test}}$  – effect of test product (Ergoferon),  $\delta$  – clinically relevant difference;

- 1.2 Clinically relevant difference value “ $\delta$ ” is considered to be equal to 20% (i.e. Ergoferon effect is supposed to be comparable to the one of oseltamivir if the effect of test product is superior to or inferior to the effect of reference product by no more than 20%);
- 1.3 The power of statistical tests ' $P = (1 - \beta)$ ' is 80% (the probability of correct rejection of the null hypothesis is 0.8);
- 1.4 The probability of type 1 error ' $\alpha$ ' is less than 5% (the probability of false acceptance of the alternative hypothesis is less than 0.05);
- 1.5 Therefore, sample size will be calculated taking into account:
- a. assumption on expected effects declared in the main efficacy criterion of the protocol;
- 1.6 calculation of sample size of groups 1 and 2 for two-sided test for final analysis will be made using the formula:

$$\mathbf{N_1=N_2=(p_a(1 - p_a) + p_b(1 - p_b)) I,}$$

where  $\mathbf{N_1}$  and  $\mathbf{N_2}$  – samples sizes in Ergoferon and Oseltamivir groups

$\mathbf{p_a}$  and  $\mathbf{p_b}$  – expected proportions of the patients with recovery/improvement in these groups

$\mathbf{I}$  – Fisher's information detected using the formula:

$$\mathbf{I=(z_\alpha + z_\beta)^2/(\theta - \delta)^2,}$$

where  $\mathbf{z_\alpha}$  and  $\mathbf{z_\beta}$  – tabular values of z-test for  $\alpha$  and  $\beta$ ,  $\theta$  – difference between proportions ( $\mathbf{p_a - p_b}$ ),  $\delta$  – clinically relevant difference;

- 1.7 final sample size will be determined using the formula:

$$\mathbf{N_F = N / (1 - K_B),}$$

---

 SAS/STAT(R) 9.2 User's Guide, Second Edition.

[http://support.sas.com/documentation/cdl/en/statug/63033/HTML/default/viewer.htm#statug\\_seqdesign sect027.htm](http://support.sas.com/documentation/cdl/en/statug/63033/HTML/default/viewer.htm#statug_seqdesign sect027.htm)

1.8 where  $N_F$  – final sample size;  $N$  – result of calculation in cl. 1.6, i.e. scheduled number of patients completing the study per protocol;  $C_w$  – withdrawal coefficient.

2. Assumptions on expected clinical study effects:

2.1 The difference between proportions of the patients with recovery/improvement on days 2-7 (according to the patient’s diary) and on days 3 and 7 (according to objective medical examination) in Ergoferon group and Oseltamivir is expected to be  $\geq 0\%$ .

The minimum size of each group will be determined as follows:

Number of patients	Final analysis
Number of patients in both groups	158
including	
- number of patients in Ergoferon groups	79
- number of patients in Oseltamivir group	79

Taking into account that potential withdrawal of 20% patients during the screening and during the study, at least 198 patients (99 in Ergoferon and Oseltamivir group) should sign informed consent.

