## Study purposes

- To assess the efficacy of Ergoferon in the treatment of influenza.
- To compare the efficacy of Ergoferon and Oseltamivir in the treatment of influenza.
- To assess the safety of Ergoferon in the treatment of influenza.

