## **Study design**

Study design: an open-label, comparative, randomized, parallel group clinical study to evaluate efficacy of the study treatment.

The study will enroll outpatient subjects of either gender aged 18-70 years old inclusively with clinical manifestations of influenza during seasonal morbidity seeking medical advice within the first two days of the disease.

After signing informed consent to participate in the clinical study baseline examination will be initiated including nasal swab for rapid diagnosis and verification of influenza as the cause of the disease. In case of positive result of immunochromatographic test the patient will be enrolled. In case of negative result of rapid test the patient will be enrolled provided that (1) he/she has clinical manifestations of typical influenza; (2) the history evidences contact with a patient with influenza; (3) the region has influenza epidemics. Additionally, at the screening (Day 1) all patients regardless of the results of rapid test will provide nasopharyngeal swabs for further PCR diagnosis and identification of RNA of influenza A and B virus, thermometry, history collection, evaluation of vital signs, physical examination will be performed and concomitant therapy will be recorded. Females of childbearing potential will undergo pregnancy test. If inclusion criteria are met and non-inclusion criteria are absent (Day 1) the patient will be enrolled in the trial and randomized into one of the two groups: group 1 will receive Ergoferon as per the selected dosing regimen for 5 days; group 2 will be treated with Oseltamivir at 75 mg twice a day for 5 days.

At Day 1 visit the patient will receive the study product and an antipyretic product approved by the study protocol.

The patient will receive the diary in which he/she will have to record axillary body temperature (measured by non-mercuric Geratherm Classic thermometer ) in the morning and evening as well as intensity of the disease symptoms and number of doses of the antipyretic product. The investigator will train the patient concerning the diary filling.

In total 3 visits (Days 1, 3 and 7) will be made by the patient/investigator during the treatment and follow-up period, on day 5 an additional visit will be made for nasopharyngeal swabs.

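### Item 1.2 reads meeting a 20-point margin as a comparable effect, but with no stated oseltamivir effect and no untreated arm it shows only that a deficit of 20 points or more is excluded

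*Combined protocol and SAP*

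**What the plan says.** All references are to the Combined protocol and SAP.

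- **Design.** Study design describes the trial thus: "Study design: an open-label, comparative, randomized, parallel group clinical study to evaluate efficacy of the study treatment". There are two arms, Ergoferon and oseltamivir, and no placebo or untreated group.
- **Purposes.** The first purpose is to assess Ergoferon's efficacy in influenza. The second is "To compare the efficacy of Ergoferon and Oseltamivir in the treatment of influenza".
- **Hypothesis.** Evaluation of sample size, item 1.1, assumes that oseltamivir has no clinically relevant superiority "over test product (Ergoferon) is assumed, thus statistically meeting Non-Inferiority design". The null is a control-minus-test difference of δ or more; the alternative is a difference below δ.
- **Margin.** In item 1.2, δ "is considered to be equal to 20"%. Item 1.6 subtracts δ from a difference of proportions, so these are absolute percentage points.
- **Interpretation.** The bracket in item 1.2 then says: "Ergoferon effect is supposed to be comparable to the one of oseltamivir if the effect of test product is superior to or inferior to" the reference effect by no more than 20%.
- **Other inputs.** Power is 80%. Alpha is below 5% (item 1.4), and item 1.6 refers to a two-sided test. The expected proportions appear only as symbols. The only effect assumption (item 2.1) is a between-group difference of at least 0%.
- **Endpoint.** The primary outcome is the proportion recovered or improved on each of days 2-7 by diary, and on days 3 and 7 by physician examination.

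**The concern.** A non-inferiority margin supports a statement about effect only when it is smaller than the comparator's own advantage over no treatment on the same readout. The plan gives no such advantage, no untreated recovery proportion and no clinical rationale for 20 points, and two active arms cannot supply them. The patients are outpatients without severe influenza, scored over one week, so some successes in either arm may owe nothing to the drug.

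The bracket also goes beyond the hypothesis in a second way. It describes a two-sided band (neither better nor worse by more than 20%), whereas the alternative in item 1.1 bounds only the deficit.

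At stake is how the primary result is read. The trial could report an effect comparable to oseltamivir from data that fit a product with no effect.

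**Working it through.** **1. The plan's own figure.** Item 1.6 with θ = 0 and a common proportion p is n = 2p(1−p)(z_α + z_β)²/δ² per arm, with δ = 0.20 and z_β = 0.842. The documents give no p, so it has to be assumed.

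| Alpha | p (assumed) | Formula | n per arm |
|---|---|---|---|
| two-sided 5% | 0.725 | 78.24 | 79 |
| two-sided 5% | 0.50 | 98.11 | 99 |
| one-sided 5% | 0.50 | 77.28 | 78 |

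So 79 per arm can be reached but not reproduced from stated inputs, and the reading of alpha stays open. With 20% withdrawal, 158/(1 − 0.2) = 197.5, which rounds up to the stated 198.

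**2. What the test excludes.** Rejecting the null in item 1.1 excludes (oseltamivir − Ergoferon) ≥ 20 points. Let A be oseltamivir's advantage over no treatment on the same day. An inert product has a true deficit of A. If A is below 20 points, an inert product satisfies the alternative hypothesis. The plan does not state A. This step needs no model.

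**3. How large must oseltamivir's effect be? (illustration)** Assume proportional recovery hazards with ratio r (oseltamivir to inert) and that recovery, once reached, lasts. Neither assumption is in the documents.

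- If S is the proportion not yet recovered on an inert product, the gap is S − S^r.
- Setting the derivative to zero gives S = r^(−1/(r−1)), so the largest possible gap is r^(−1/(r−1)) − r^(−r/(r−1)).
- Example, r = 1.5: S = 1.5^(−2) = 0.444 and S^1.5 = 0.296, a gap of 14.8 points.
- The largest gap equals 20 points at r = 1.734, where S = 0.472 and S^r = 0.272. That is 52.8% versus 72.8% recovered.
- On the proportion scale this same point is 72.8/52.8 = 1.38, a 38% relative rise.

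**4. Chance of declaring an inert product non-inferior.** Exact binomial enumeration, 79 per arm, non-inferior when the upper Newcombe limit for oseltamivir minus inert is below 20 points, at the largest-gap day. The Newcombe interval is an assumption.

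| r | Inert vs oseltamivir recovered | Gap (points) | Two-sided 95% interval | One-sided 5% |
|---|---|---|---|---|
| 1.25 | 59.0% vs 67.2% | 8.2 | 37% | 49% |
| 1.3 | 58.3% vs 67.9% | 9.6 | 30% | 41% |
| 1.5 | 55.6% vs 70.4% | 14.8 | 11% | 18% |
| 1.73 | 52.8% vs 72.8% | 20.0 | 3% | 6% |

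The largest-gap day is not exactly where the probability is lowest. Over all recovery levels, the two-sided minimum is 34% at r = 1.25 and 28% at r = 1.3, so the table is close to the best case but is not a strict floor.

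**The case against.** - **The text is a protocol summary, and the bracket sits among sample-size assumptions.** A rationale may exist in a fuller protocol, and no separate reporting rule is given. That stands: the claim is only that none appears in the text supplied. But item 1.2 is complete as written, and it is the only statement of what meeting the margin means.
- **The 73% depends on a model.** This also stands. The endpoint is a proportion assessed afresh each day, so relapse is possible and no hazard is modelled. A reader might take 73% as the rise needed in the proportion recovered, which would be wrong: it is 38% at the critical point, and a 20-point gap is a 25% rise from a baseline of 80%. Nor is the threshold obviously out of reach. For Weibull recovery curves of shape 2 or 3, a hazard ratio of 1.73 means recovery times only 24% or 17% shorter.
- **Alpha is not broken.** A reader might infer that the type 1 error in item 1.4 is miscontrolled. The documents do not support that. It applies to a null of a 20-point deficit, and at that deficit the calculation gives about 3% (two-sided) or 6% (one-sided), close to the nominal 2.5% and 5%. The fault lies in the interpretation attached to rejecting that null.
- **Inside the margin is not the same as declared non-inferior.** Correct; step 4 is there to separate the two.

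**Conclusion.** The point holds in this form. Item 1.2 attaches to a 20-point margin a conclusion that the test cannot deliver, because no oseltamivir-versus-untreated effect is stated, no untreated arm exists, and the hypothesis bounds only one direction. That rests on the text alone.

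Its size can only be illustrated. Under the assumed hazard model, an inert product would be called non-inferior on the largest-gap day with a chance of 37% down to 3% as the hazard ratio goes from 1.25 to 1.73, or 49% down to 6% if alpha is one-sided 5%. The true oseltamivir effect on this readout is not in the documents, so which row applies is unknown. A reader might go further and infer that Ergoferon is inert, or that oseltamivir's effect is smaller than the margin; nothing in the documents shows either.

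**What to change.** Replace the bracket in item 1.2 with wording such as: *If the margin is met, the conclusion is that Ergoferon is not worse than oseltamivir by 20 percentage points or more; this alone is not evidence that Ergoferon is effective or that the effects are comparable.* Report the upper confidence limit of the oseltamivir-minus-Ergoferon difference as the largest deficit not excluded.

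The cost is wording and a weaker headline conclusion; no patients are added. The change also makes plain that the first study purpose is not answered by the non-inferiority test alone.

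A rule that a fixed share of the oseltamivir effect, such as half, must be preserved is not part of this fix. The documents give no basis for the share. If the effect were 15 points (assumed), half would be 7.5 points, and power at 79 per arm with p = 0.72 (assumed) and two-sided 5% would be Φ(0.075/√(2 × 0.72 × 0.28/79) − 1.96), about 18%.

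### No planned analysis tests the 20-point non-inferiority hypothesis in item 1.1, and the wording of items 1.2 and 1.6 conflicts with it; 79 per arm is not shown to be wrong

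*Combined protocol and SAP*

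**What the plan says.** All numbered items are in Evaluation of sample size.

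- **1.1** assumes no clinically relevant superiority of oseltamivir, "thus statistically meeting Non-Inferiority design". The null is oseltamivir minus Ergoferon at or above delta; the alternative is below delta.
- **1.2** sets delta at 20% and explains it as Ergoferon being "superior to or inferior to the effect of reference product by no more than 20" percent.
- **1.3** sets power at 80%: "the probability of correct rejection of the null hypothesis is 0.8".
- **1.4** sets alpha: "the probability of false acceptance of the alternative hypothesis is less than 0.05". It does not state sidedness.
- **1.6** says: "calculation of sample size of groups 1 and 2 for two-sided test for final analysis will be made using the formula". The formula prints z_alpha with no value and needs p_a and p_b.
- **1.5a** takes these from an "assumption on expected effects declared in the main efficacy criterion of the protocol", but Primary Outcome Measure states no rates. Item 2.1 gives only a difference, over diary days 2-7 "and on days 3 and 7 (according to objective medical examination) in Ergoferon group and Oseltamivir is expected to be" at least 0%.
- **1.8** defines N as the "scheduled number of patients completing the study per protocol". The result is 79 per arm.

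Statistical criteria describes comparisons of proportions as assessments of equality or inequality. Non-parametric tests lists chi-square, Fisher's exact, Cochran-Mantel-Haenszel and survival analysis. Data presentation adds per-visit frequency tables. The 20% margin appears in none of these three sections.

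**The concern.** The trial is sized to reject a null that oseltamivir is better by 20 points or more. Chi-square, Fisher and Cochran-Mantel-Haenszel test a null of no difference. A significant result does not show that the difference is below 20 points, and a non-significant one does not exclude a deficit of 20 points. Survival analysis as listed carries no margin either. The comparison with oseltamivir, a stated study purpose, therefore has no named analysis that can deliver the conclusion the sample size was built for.

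The two conflicting wordings then leave room for choice. Two-sided in 1.6 could mean a 95% interval, while 1.1 and 1.4 fit a one-sided 5% test (90% interval). Item 1.2 could be quoted as requiring that Ergoferon not be better by more than 20 points. The study is open-label, so the rule should be fixed before results are visible.

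**Working it through.** **Inputs.** From the plan: delta = 0.20 (read as percentage points, because the formula subtracts it from a difference in proportions), power 80% (z_beta = 0.8416), 79 per arm. Assumed: true difference theta = 0 (the plan says at least 0%) and a common rate p, shown over a range because the plan gives none.

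**The plan's own figure.** 79 cannot be reproduced without p_a and p_b. The withdrawal step does reproduce: 79/0.8 = 98.75, so 99; 158/0.8 = 197.5, so 198.

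**Size.** N = 2p(1-p) × I, with I = (z_alpha + z_beta)²/0.20².

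- One-sided 5%: I = (1.6449 + 0.8416)²/0.04 = 154.56. The maximum is at p = 0.5: 0.5 × 154.56 = 77.3, so 78.
- Two-sided 5%: I = (1.960 + 0.8416)²/0.04 = 196.22. N is 98.1 at p = 0.5, 82.4 at 0.3/0.7 and 79.1 at 0.28/0.72.

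So 79 fits one-sided 5% at the least favourable rate, and two-sided 5% only at about 0.28/0.72.

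**Power of 79 per arm.** Power = Φ(0.20/SE − z_alpha), SE = √(2p(1-p)/79).

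| p | 0.20/SE | one-sided 5% | two-sided 5% |
|---|---|---|---|
| 0.5 | 2.514 | 80.8% | 71.0% |
| 0.4/0.6 | 2.566 | 82.1% | 72.8% |
| 0.3/0.7 | 2.743 | 86.4% | 78.3% |
| 0.28/0.72 | 2.800 | 87.6% | 79.9% |
| 0.2/0.8 | 3.143 | 93.3% | 88.1% |

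Exact binomial enumeration with Wald limits at p = 0.5 gives 80.9% and 71.1%.

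The two-sided figures rise if Ergoferon is truly better. With rates 0.53 v 0.50, SE = √((0.2491 + 0.25)/79) = 0.0795, and Φ(0.23/0.0795 − 1.96) is about 82%.

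**What an equality test would let through.** Exact probability that chi-square (two-sided 5%, no continuity correction, 79 per arm) is non-significant when Ergoferon is truly 20 points worse:

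| Oseltamivir rate | 0.5 | 0.6 | 0.7 | 0.8 | 0.9 |
|---|---|---|---|---|---|
| Non-significant | 27.0% | 29.5% | 27.0% | 20.5% | 9.8% |

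For comparison, an upper 90% Wald limit below 20 points gives 4.6-5.0% false non-inferiority at rates 0.5-0.8 and 5.2% at 0.9. A 95% interval gives 2.3-2.5% at rates 0.5-0.8.

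**Three possible results** (oseltamivir v Ergoferon, Wald limits):

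- 45/79 v 34/79: difference 0.139, SE 0.0788; chi-square p = 0.080. Upper limit 26.9 points (90%) or 29.4 (95%). No significant difference, yet non-inferiority is not shown on either interval.
- 40/79 v 36/79: difference 0.0506, SE 0.0794. Upper limit 18.1 points (90%, non-inferior) or 20.6 (95%, not shown).
- 36/79 v 46/79: 90% interval −25.6 to 0.3 points. This meets 1.1 but goes outside ±20 if 1.2 is taken literally.

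**The case against.** The strongest reply is that sidedness is hardly open. Item 1.1 is explicit and one-directional, the parenthesis in 1.4 describes the one-directional error for that alternative, the formula prints z_alpha, and 79 covers the 78 needed at one-sided 5% for any rate. Two-sided in 1.6 is then the outlier. This stands, and it is why 79 should not be called too small. The outlying wording still has to be changed.

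Item 1.2 is an explanatory gloss on delta, not a second hypothesis. This also stands. A reader might infer an equivalence trial, for which power at p = 0.5 would be 2Φ(2.514 − 1.645) − 1 = 61.5%. The formal hypotheses in 1.1 do not support that.

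A reader might also infer that the sponsor intends to treat a non-significant chi-square as proof of comparability. No section says so; the 20-29% is conditional on that use and shrinks at high rates.

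The document calls itself a protocol summary, so the rates, and possibly a margin-based analysis, may be stated elsewhere. That is fair for p_a and p_b. It does not remove the conflict among 1.1, 1.2 and 1.6, and the list of tests given here omits the one that the hypothesis needs.

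Finally, more than 79 per arm may be analysed. On a 95% interval at p = 0.5, power is 76.5% with 90 per arm (assumed) and about 80% with 99. The 198 counts consents and allows for screening losses, but it is a minimum, so 99 is not a ceiling.

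**Conclusion.** The gap is real and does not depend on any assumed rate: no analysis named in this document can reject the null in 1.1, and the wording of 1.2 and 1.6 conflicts with it. If equality tests filled the gap, the risk of passing a true 20-point deficit would be about 20-29% at oseltamivir rates of 0.5-0.8 and about 10% at 0.9, against the stated error below 5%.

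The documents do not support the stronger conclusion that the trial is underpowered. At one-sided 5% and theta = 0, 79 completers per arm give at least 80.8% power at every common rate, for a single comparison. Power falls short only if two-sided means a 95% interval, the rate lies between about 0.28 and 0.72, and Ergoferon has no true advantage.

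This should be corrected, but it is a matter of specification rather than of trial size.

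**What to change.** State one primary analysis under Statistical criteria and Non-parametric tests: non-inferiority is concluded if the upper confidence limit for oseltamivir minus Ergoferon, in the proportion with recovery/improvement at one named day and from one named source (diary or physician), is below 20 points. Keep the equality tests as supportive. Reword 1.2 so that it limits only how far Ergoferon may fall below oseltamivir, and make 1.4 and 1.6 state the same alpha and sidedness. Then choose one:

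- **(a)** One-sided 5% (90% interval). 79 completers per arm support 80% power for that single comparison. Item 1.4 must then say 5% rather than below 5%. The cost is openly accepting a 5% rather than 2.5% risk of false non-inferiority; Wald limits can slightly exceed 5% at high rates (5.2% at an oseltamivir rate of 0.9).
- **(b)** Two-sided 5% (95% interval). State p_a and p_b for the chosen day and source, and restate the power of 79 completers at those rates. The cost is that item 1.3 may have to give less than 80%, as low as about 71% near a rate of 0.5 with no true difference.

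Either way the change is wording plus one confidence interval, with no extra patients and no new data.
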